**TEMPLATE: RESEARCH PROTOCOL**

| NUMBER | ACTIVE DATE | PAGE |
|---------|-------------|----------|
| HRP-503 | 02-04-2020 | 36 of 40 |

34.0 EXTERNAL LOCATIONS**34.1 List any external locations to UC or its affiliates.**

Not Applicable..

# The Effect of Immediate Versus Delayed Debriefing on Basic Life Support Competence In Undergraduate Nursing Students.

NCT06624449

October 5, 2023

*[name] ([name])*

[Company Name] | [Company Address]

The statistical analysis was conducted using JMP Pro 16 software. Descriptive statistics for the students' demographics were calculated, including means, standard deviations, and frequencies. A Paired t-test was used to determine the differences between the experimental and control groups before and after the intervention. An independent t-test was applied to examine differences in BLS competence levels between the two groups. A p-value of less than 0.05 was considered statistically significant, with a 95% confidence interval. If the p-value was below 0.05, the null hypothesis would be rejected; if it exceeded 0.05, we would fail to reject the null hypothesis. Independent t-tests were also used to compare the mean debriefing experience scores between the hot and cold debriefing groups, with p-values below 0.05 considered statistically significant.

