| 1.0 OBJECTIVES | 1.1 Describe the purpose, specific aims, or objectives. For phase 1, quantitative part: Specific aim 1: Identify the efficacy of cold versus hot debriefing in (Basic Life Support) BLS training for undergraduate nursing students' BLS competence. Specific aim 2: Assess the impact of hot and cold debriefing on senior or third year nursing students' debriefing experience. For phase 2 qualitative part: Specific aim 3: Explore the experiences of undergraduate nursing students who used the cold and hot debriefing style in BLS training. Specific aim 4: To identify the similarities and differences in reflective thinking between undergraduate nursing students who used hot and cold debriefing. |
| | 1.2 Describe the hypotheses to be tested. Hypothesis 1a: In both cold and hot debriefing groups, there is a significant difference in the BLS competence of undergraduate nursing students between pre-intervention and post-intervention. Hypothesis 1b: Undergraduate nursing students who have cold debriefing will show greater BLS competence than those who receive hot debriefing. Hypothesis 2: There is a significant difference in debriefing experience scores of undergraduate nursing students between hot and cold debriefing. |
| 2.0 BACKGROUND | 2.1 Describe the relevant prior experience and gaps in the current knowledge. Cardiac arrest is one of the leading causes of death globally; the number of out-of-hospital cardiac arrests in the U.S. exceeds 356,000 per year. Nearly 90% of them are fatal (Tsao et al., 2022). Over the years, cardiopulmonary resuscitation (CPR) has been proven to be associated with patient survival (Oermann et al., 2020). The American Heart Association (AHA) and European Resuscitation Council recommend high-quality CPR following a cardiac arrest to improve patient outcomes and survival rates (Cheng et al., 2018; Wolfe et al., 2014). Basic Life Support (BLS) is an essential element in simulation for nursing students. The primary goal of BLS is to enable nurses to provide resuscitation to individuals experiencing cardiac or pulmonary arrests (The Association for the Advancement of Sustainability, 2019). According to the literature, even if undergraduate nursing students are BLS certified, they frequently lack the comprehensive knowledge and competence of BLS (Oermann et al., 2020). This lack of knowledge and competence can be |

TEMPLATE: RESEARCH PROTOCOL

| NUMBER | ACTIVE DATE | PAGE |
|---------|-------------|---------|

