| | 
6.1 Thoroughly describe the study design.
 
This study consists of two phases. Phase 1 will be a randomized controlled trial (RCT). Having a controlled group is the gold standard to measure the efficacy of an intervention (Polit & Beck, 2021). RCTs provide the most persuasive evidence on whether one variable has a causal influence on another. RCTs' main strength is the certainty with which causal links may be determined. Kolb's learning theory serves as the underpinning for this study (Kolb & Kolb, 2009; Kolb, 1984).
 
Manipulation: The researcher will do a cold debriefing (after one-day post-simulation) for undergraduate nursing students in the intervention group.
 
Control: The control group will do a hot debriefing (immediately after the simulation).
 
Randomization: The researcher will assign the participants to a control or experimental based on number generator.
 
Once participants complete Phase 1, we will record their progress on REDCap. If they chose to only participate in Phase 1, we will mark their status as "completed" on REDCap. If they expressed interest in Phase 2, we will randomly select 16 participants from the pool based on a number generator and update their status on REDCap for Phase 2.
 
Outcome: The study outcome is BLS competence level. The competence level will be measured AHA (2020) BLS competency Checklist. First, the control and experiment groups will complete a pre-test on BLS competence. Both groups will do a pre-test. After finishing
 |

TEMPLATE: RESEARCH PROTOCOL

| NUMBER | ACTIVE DATE | PAGE |
|---------|-------------|----------|
| HRP-503 | 02-04-2020 | 10 of 40 |

the pre-test, we will do the randomization process. Then the intervention group will receive (cold debriefing); the control group will have the (hot debriefing). Both groups will do the post-test immediately after the debriefing session and another post-test after 24 hours of the first post-test.

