| 17.0 DATA MANAGEMENT AND CONFIDENTIALITY | 17.1 Describe the data analysis plan, including any statistical procedures or power analyses. |
| | For quantitative phase 1, Statistical power G*Power 3.1 was used to determine sample size based on a 2-tailed, two-way repeated measure ANOVA for the design, a type I error of 0.05, a statistical power of 80% (type II error), and a large effect size of eta square .25-.99 (Faul et al., 2007). Based on the literature, a large effect size is appropriate for the use of simulation (Padilha et al., 2019; Pauly-O'Neill, 2009). Based on G*Power 3.1, the recommended sample size will be 26 participants in each group. Still, because there is a possibility that participants may withdraw from the study, the total number will be 30 participants in each group. There is a total of 183 eligible participants. |
| | 
Statistical Plan
 
The statistical analysis will be used by JMP Pro 16 software. The descriptive analysis for students' demographics will be computed to describe means, standard deviations, and frequencies. For hypothesis 1a, the appropriate statistical analysis test will be the repeated measure ANOVA to find the difference between the experimental and control group in pre and post-intervention. For hypothesis 1b, an independent t-test will be used to find the differences between the two groups in the BLS competence level. The p-value of <0.05 will be considered statistically significant, and the confidence interval will be set at 95%. If the p-value is less than 0.05, we will reject the null hypothesis; If the p-value is more than 0.05, we will fail to reject the null hypothesis. For hypothesis 2, an independent t-test will be used to compare means between hot debriefing and cold debriefing groups. DES with P-values <0.05 will be considered statistically significant.
 |

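### The SAP replaces the planned repeated-measures ANOVA with a paired t-test worded as a between-arm comparison, and neither document names the post-test or the score that decides hypothesis 1b

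*SAP*

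**What the plan says.** Protocol 1.2 separates two BLS questions. Hypothesis 1a is about change from before to after the intervention: "In both cold and hot debriefing groups, there is a significant difference in the BLS competence of undergraduate nursing students". Hypothesis 1b is that cold debriefing gives greater competence than hot; it names no occasion.

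Protocol 17.1 assigns a test to each. For 1a, "the appropriate statistical analysis test will be the repeated measure ANOVA to find the difference between the experimental and control group", before and after the intervention. For 1b, "For hypothesis 1b, an independent t-test will be used to find the differences between the two groups in the BLS competence level". The sample size is based on a "two-way repeated measure ANOVA for the design" with "a large effect size of eta square .25-.99", giving 26 per group, raised to 30 for withdrawals.

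Protocol 6.1 sets three BLS assessments, a pre-test and two post-tests: "Both groups will do the post-test immediately after the debriefing session and another post-test after 24 hours of the first post-test". Protocol 5.1 defines the primary endpoint as completion of phase 1, so it does not choose between the post-tests.

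The SAP is one paragraph, in the past tense, dated October 5, 2023. It reports: "A Paired t-test was used to determine the differences between the experimental and control groups before and after the intervention". For the arms it says: "An independent t-test was applied to examine differences in BLS competence levels between the two groups". It mentions neither the ANOVA nor a reason for the change.

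**The concern.** There are two defects. First, the planned method for hypothesis 1a was replaced without explanation, and the replacement is described as something it cannot be. A reader could take a gain within one arm as a finding about hot versus cold. The documents also do not show whether the choice was made before data were seen: the SAP's date falls inside the planned enrolment window (Protocol 9.2, 08/24/23 to 11/01/23), but its text reports completed work.

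Second, hypothesis 1b is the only randomised comparison of BLS competence, and its test is incompletely defined. With two post-tests and two possible scores, a reader cannot tell which result decides it or how the 24-hour test is used. That leaves room to choose after the results are known.

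**Working it through.** **1. What a paired t-test can test.** It works on differences within one student, post-test minus pre-test. Protocol 6.1 randomises different students to the two arms, so no pairing runs across arms. Run separately by arm, the test answers 1a. With two occasions in a single arm it is the same test as a repeated-measures ANOVA (F = t²), so 1a loses no validity if it was run that way. The SAP does not say that it was run by arm or which post-test was paired with baseline.

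The protocol's similar between-group wording could at least describe a group-by-time term in a two-way ANOVA. The SAP's wording cannot describe a paired t-test.

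**2. Why two within-arm results do not compare the arms.** Suppose the true gain is equal in both arms and each paired test has power p. Exactly one arm is then significant with probability 2p(1−p). That is 2 × 0.8 × 0.2 = 0.32 at an assumed p of 0.8, and 0.50 at p = 0.5.

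**3. The plan's 26 per group.** Eta squared .25 gives f = √(.25/.75) = 0.577. A two-group repeated-measures ANOVA at 80% power and alpha 0.05 then needs 4 to 26 students in total, over 2 or 3 occasions, any effect, and correlations from 0 to 0.99. That does not reproduce 52. A two-sided independent t-test at d = 0.8 (assumed) gives exactly 26 per arm, with power 80.7%. The calculations below therefore use 26 per arm and 0.8 SD.

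**4. If either post-test may decide 1b at 0.05.** With no true difference, the false-positive rate is 1 − P(|Z₁| < 1.96 and |Z₂| < 1.96). For independent tests this is 1 − 0.95² = 9.75%. At assumed correlations of 0.3, 0.5, 0.7 and 0.9 it is 9.5%, 9.1%, 8.3% and 7.0%. Holm holds it at or below 5%, but its first step uses 0.025. At that level a single post-test has 71.6% power, against 80.7% at 0.05.

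**5. Value of the baseline score.** Let r be the correlation of baseline with the post-test, n = 26 per arm, and SD = 1.

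- Post-score t-test: SE = √(2/26) = 0.277, df 50, half-width 2.009 × 0.277 = 0.557 SD.
- Change-score t-test (equal variances): SE = √[(2/26) × 2(1−r)], df 50.
- ANCOVA: SE = √[(2/26)(1−r²)(1 + 1/48)], df 49. At r = 0.5 this is √(0.0769 × 0.75 × 1.0208) = 0.243, half-width 2.010 × 0.243 = 0.488 SD.

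| Assumed r | Post-score power | Change-score power | ANCOVA power | ANCOVA 95% CI half-width (SD) |
|---|---|---|---|---|
| 0 | 80.7% | 51.6% | 79.9% | 0.563 |
| 0.1 | 80.7% | 55.9% | 80.3% | 0.560 |
| 0.3 | 80.7% | 66.7% | 83.5% | 0.537 |
| 0.5 | 80.7% | 80.7% | 89.8% | 0.488 |
| 0.7 | 80.7% | 95.5% | 97.5% | 0.402 |

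ANCOVA beats the change score at every r shown. It beats the post-score test once r exceeds about 0.15, and below that the loss is under one percentage point of power.

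**The case against.** The strongest reply is that little is broken. The SAP's next sentence gives a separate between-arm test, and hypothesis 1a is plainly worded as pre versus post, so a careful reader would assign the paired test to 1a. The loose wording comes from the protocol. The independent t-test for 1b is carried over from the protocol and is valid under randomisation, apart from any clustering by debriefing group. Much of this stands, and it makes the first defect one of wording and disclosure. It does not restore the group-by-time analysis over three occasions, and it does not name the post-test or score for 1b.

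Several stronger readings are tempting, and the documents do not support them:

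- **The 1b test ignores baseline.** A reader might infer this, but a change score is not excluded. All that can be said is that the score is unstated and no covariate use is described.
- **The error rate is already inflated.** It rises only if either post-test may count, and nothing says so.
- **The method was changed after seeing results.** The past tense and the date leave the timing open.
- **The swap leaves the trial too small.** The figure of 26 does not follow from the stated ANOVA inputs, but it fits the 1b t-test at 0.8 SD. Eta squared .25 is not tied to any named effect, so it cannot serve as the assumed size for 1b.

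**Conclusion.** The point holds and should be fixed. The text alone establishes the unexplained change of method, the between-arm wording of a within-person test, the loss of the only planned method able to use all three occasions, and the absence of a named post-test and score for 1b. The hypotheses are unnumbered in the SAP, so linking its paired test to 1a rests on order and wording.

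The sizes are conditional. The 7% to 9.5% error rate assumes that either post-test could count. The power and precision figures assume 26 per arm, a 0.8 SD difference, normal scores and independent students; the documents give no correlation. Protocol 6.2 describes group debriefing, so students may be clustered. That is a secondary point of unknown size, because neither group size nor intraclass correlation is given.

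**What to change.** 1. Reword the SAP sentence and the matching sentence in Protocol 17.1. The paired test is the within-arm pre/post change for 1a, with a 95% CI and its post-test named. State that it is not evidence of hot versus cold and cannot be separated from retesting, since the same simulation and checklist are repeated (Protocol 6.2).
2. Name the one post-test and the score that carry 1b, and report the other post-test as secondary. If both carry it, use Holm and state its cost in power.
3. Estimate the 1b contrast with baseline BLS as a covariate, with a 95% CI: ANCOVA at the named post-test, or a mixed model with group by time over both post-tests. First reconcile Protocol 6.1, which randomises after the pre-test, with 6.2, which assigns before it. The principal investigator assigns (6.2) and may also score (6.5). If baseline may have been scored with allocation known, report the unadjusted result alongside.
4. State the departure from the planned ANOVA and its reason. Report any choice made after data were seen as a disclosed departure, not as prespecified.
5. Add a sensitivity analysis for debriefing group if membership was recorded; otherwise state the limitation.

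The cost is a few sentences and a few lines of analysis, with no new visits, because baseline and both post-tests are already collected. Adjustment uses one degree of freedom. Step 5 needs group membership, which the documents do not say is recorded.
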